7.2. Research Objectives

The following matters will be investigated in patients receiving BESPONSA under actual conditions of use after marketing:

(1) Occurrence of adverse events (AEs) (including the following evaluations):

Background characteristics possibly affecting the onset of liver disorder including VOD/SOS, myelosuppression, infections and hemorrhage, and grade ≥ 3 events based on the CTCAE v4.0 as well as risk factors for early death of HSCT patients after BESPONSA treatment

(2) Efficacy (hematologic remission rate and survival)

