8.2. Setting

All patients receiving BESPONSA will be included in this investigation.

PFIZER CONFIDENTIAL

CT24-WI-JPN-GPSP01-RF09 8.0 Non-Interventional Study Protocol Template for Secondary Data Collection

Study 01-Nov-2023

Page 13 of 33

Inotuzumab

B1931024 NON-INTERVENTIONAL STUDY PROTOCOL

Amended 8, 12 December 2023

[INDICATION]

Relapsed or refractory CD22-positive ALL

[DOSAGE AND ADMINISTRATION]

The usual dosage for adults is 0.8 mg/m² (body surface area) of inotuzumab ozogamicin (genetical recombination) on Day 1 and 0.5 mg/m² (body surface area) on Days 8 and 15 once daily by intravenous infusion over at least 1 hour followed by a treatment-free interval. The length of cycle is 21 to 28 days for Cycle 1 and 28 days for Cycles 2 and subsequent cycles. The treatment should be repeated. The number of cycles should be decided while taking account of the schedule of HSCT. The dose should be decreased as necessary according to the patient's condition.

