#### 8.1.3. Binary variables

For binary variables, patients falling into each binary category will be summarized in terms of frequency (n) and proportion. If a confidence interval (CI) is determined for a proportion, the two-sided 95% CI will be determined using the exact method.

For a comparison of proportion between subgroups, the risk ratio (RR) and its 95% CI will be determined. In addition, the RRs and their 95% CIs will be graphically presented.

For statistical tests, Fisher's exact test will be performed to test correlations in nominal scale data, and Cochran-Armitage test (exact method) to test correlations in ordinal scale data. If, however, it is difficult to use the exact method, chi-square test or Cochran-Armitage test with normal approximation will be used as an alternative to the exact method.

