### **8.2.3. Safety analyses**

Adverse drug reactions (ADRs) and adverse events (AEs) that occurred in the following periods will be collected for summary: for ADRs and AEs other than VOD/SOS, those that occurred from the start of this drug to 28 days after the final dose of this drug will be collected; for ADRs and AEs of VOD/SOS in patients who did not undergo HSCT within 52 weeks after the start of this drug, those that occurred within 52 weeks after the start of this drug will be collected; for ADRs and AEs of VOD/SOS in patients who underwent HSCT within 52 weeks after the start of this drug, those that occurred within 52 weeks after the last HSCT will be collected. The listings will include all events reported in this survey.

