#### 8.2.3.4. Subgroup analyses

Patients who experienced at least one AR will be summarized in terms of n and proportion by each of the following factors selected from those specified in Section 5.4. To investigate the correlation between patient characteristics and occurrence of ADRs, statistical tests specified in Section 8.1.3 and risk ratio estimation will be performed.

- Age [ $< 15$  years,  $\geq 15$  to  $< 65$  years,  $\geq 65$  years]
- Age [ $< 18$  years,  $\geq 18$  to  $< 55$  years,  $\geq 55$  years]
- Age [ $< 15$  years,  $\geq 15$  years to  $< 40$  years,  $\geq 40$  years]
- Disease name
- Chromosome karyotype
- Chromosome karyotype \* Philadelphia chromosome is considered positive if the chromosome karyotype is t(9;22).
- Hepatic impairment
- Renal impairment
- Medical history (past) - VOD/SOS
- Medical history (past) - GVHD
- Medical history (past) - Hepatitis or hepatic disease
- Medical history (present) - VOD/SOS
- Medical history (present) - GVHD
- Medical history (present) - Hepatitis or hepatic disease

- ECOG PS before the start of this drug
- AST and ALT levels immediately before the start of this drug
- $\gamma$ -GTP level immediately before the start of this drug
- Total bilirubin level immediately before the start of this drug
- Hemoglobin level immediately before the start of this drug
- Platelet count immediately before the start of this drug
- Peripheral blast count immediately before the start of this drug
- Myeloblast count immediately before the start of this drug
- Salvage line of the induction treatment with this drug
- HSCT before the start of this drug
- Pregnancy \* Pregnancy during the treatment period. Limited to cases in which information on pregnancy is collected

Furthermore, patients who experienced ADRs will be summarized in terms of n and proportion for each SOC and PT by each of the following factors selected from those specified in Section 5.4. In addition, risk ratios for the proportion of patients with ADRs for different subgroups will be determined as per Section 8.1.3 and presented graphically. If, however, there is a category with less than 10 patients and after reconsideration it is considered difficult to determine the risk ratio for the category, it will not be determined for the relevant category. To investigate the correlation between patient characteristics and occurrence of ADRs, statistical tests specified in Section 8.1.3 will be performed.

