- Age [< 15 years,  $\geq 15$  to  $< 65$  years,  $\geq 65$  years]
- Age [< 18 years,  $\geq 18$  to  $< 55$  years,  $\geq 55$  years]
- Age [< 15 years,  $\geq 15$  to  $< 40$  years,  $\geq 40$  years]
- Hepatic impairment
- Renal impairment
- HSCT before the start of this drug
- Total dose per cycle  $> 1.8$  mg/m^2
- Pregnancy \* Pregnancy during the treatment period. Limited to cases in which information on pregnancy is collected

Similarly, ADRs meeting definition of liver disorder including safety specification events of VOD/SOS will be analyzed by each of the following factors. Similar analyses will also be performed for ADRs of Grade 3 or higher based on CTCAE v4.0.

- Age [< 15 years,  $\geq 15$  to  $< 65$  years,  $\geq 65$  years]
- Age [< 18 years,  $\geq 18$  to  $< 55$  years,  $\geq 55$  years]
- Age [< 15 years,  $\geq 15$  to  $< 40$  years,  $\geq 40$  years]
- Hepatic impairment
- Medical history (past) - VOD/SOS
- Medical history (past) - Hepatitis or hepatic disease
- Medical history (present) - VOD/SOS
- Medical history (present) - Hepatitis or hepatic disease
- ECOG PS before the start of this drug

- AST and ALT levels immediately before the start of this drug
- $\gamma$ -GTP level immediately before the start of this drug
- Total bilirubin level immediately before the start of this drug
- Platelet count immediately before the start of this drug
- Peripheral blast count immediately before the start of this drug
- Salvage line of the induction treatment with this drug
- HSCT before the start of this drug

Similarly, ADRs meeting definition of safety specification events of myelosuppression will be analyzed by each of the following factors. Similar analyses will also be performed for ADRs of Grade 3 or higher based on CTCAE v4.0.

- Age [ $< 15$  years,  $\geq 15$  to  $< 65$  years,  $\geq 65$  years]
- Age [ $< 18$  years,  $\geq 18$  to  $< 55$  years,  $\geq 55$  years]
- Age [ $< 15$  years,  $\geq 15$  to  $< 40$  years,  $\geq 40$  years]
- Hepatic impairment
- Renal impairment
- Total dose per cycle  $> 1.8 \text{ mg/m}^2$
- ECOG PS before the start of this drug
- White blood cell count immediately before the start of this drug
- Neutrophil count immediately before the start of this drug
- Platelet count immediately before the start of this drug
- Salvage line of the induction treatment with this drug
- HSCT before the start of this drug

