Similarly, ADRs meeting definition of safety specification events of infection will be analyzed by each of the following factors. Similar analyses will also be performed for ADRs of Grade 3 or higher based on CTCAE v4.0.

- Age [ $< 15$  years,  $\geq 15$  to  $< 65$  years,  $\geq 65$  years]
- Age [ $< 18$  years,  $\geq 18$  to  $< 55$  years,  $\geq 55$  years]
- Age [ $< 15$  years,  $\geq 15$  to  $< 40$  years,  $\geq 40$  years]
- Hepatic impairment
- Renal impairment
- Total dose per cycle  $> 1.8 \text{ mg/m}^2$
- ECOG PS before the start of this drug
- Salvage line of the induction treatment with this drug
- HSCT before the start of this drug

Similarly, ADRs meeting definition of safety specification events of hemorrhage will be analyzed by each of the following factors. Similar analyses will also be performed for ADRs of Grade 3 or higher based on CTCAE v4.0.

- Age [ $< 15$  years,  $\geq 15$  to  $< 65$  years,  $\geq 65$  years]
- Age [ $< 18$  years,  $\geq 18$  to  $< 55$  years,  $\geq 55$  years]

- Age [ $< 15$  years,  $\geq 15$  to  $< 40$  years,  $\geq 40$  years]
- Hepatic impairment
- Renal impairment
- Total dose per cycle  $> 1.8 \text{ mg/m}^2$
- ECOG PS before the start of this drug
- Salvage line of the induction treatment with this drug
- HSCT before the start of this drug

Similarly, patients who experienced GVHD will be analyzed by each of the following factors. GVHD events included in the analysis will be events of which PT includes GVHD according to the version of MedDRA used for the analysis.

- Medical history (past) - GVHD
- Medical history (present) - GVHD

Similar analyses will be performed for serious ADRs.

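### Crude risk ratios for infection, hemorrhage and myelosuppression ADRs compare subgroups over windows that depend on cycles received, so they can show or hide a difference unrelated to on-treatment hazard

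*SAP*

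**What the plan says.** Protocol 7.2 makes it an objective to study "Background characteristics possibly affecting the onset of liver disorder including VOD/SOS, myelosuppression, infections and hemorrhage".

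SAP 8.2.3.4 takes this up class by class: "Similarly, ADRs meeting definition of safety specification events of myelosuppression will be analyzed by each of the following factors"; "Similarly, ADRs meeting definition of safety specification events of infection will be analyzed by each of the following factors"; "Similarly, ADRs meeting definition of safety specification events of hemorrhage will be analyzed by each of the following factors". Each analysis is repeated for Grade 3 or higher. The factors common to the three lists are age, hepatic and renal impairment, a total dose above 1.8 mg/m² in a cycle, ECOG PS, salvage line and prior HSCT. Myelosuppression adds baseline blood counts.

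The method carries over from the preceding ADR analysis in the same section: "risk ratios for the proportion of patients with ADRs for different subgroups will be determined as per Section 8.1.3 and presented graphically". Section 8.1.3 adds only this: "For a comparison of proportion between subgroups, the risk ratio (RR) and its 95% CI will be determined", with Fisher's exact or Cochran-Armitage tests.

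For ADRs other than VOD/SOS, SAP 8.2.3 sets the window: "those that occurred from the start of this drug to 28 days after the final dose of this drug will be collected". Treatment length is not fixed. Protocol 8.2 says: "The number of cycles should be decided while taking account of the schedule of HSCT". SAP 8.2.2 tabulates from 1 to more than 6 cycles.

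The one ADR analysis that allows for censoring is the time-to-onset analysis in SAP 8.2.3.1, censored 28 days after the final dose. It covers the whole safety set, for ADRs in at least 10% of patients, and is not split by baseline factor. Section 8.1.4 provides a Cox hazard ratio for subgroup comparisons, but 8.2.3.4 does not call it.

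**The concern.** A proportion with at least one event depends on the hazard and on how long the patient is watched. Here the length of watching is set by treatment duration. The plan has no common window, no censoring, no adjustment for exposure, and no cycle count among the factors for these three classes.

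A factor that only goes with more cycles could therefore look like a risk factor. A factor that leads to early stopping could look harmless despite a higher hazard. Finding such factors is a stated objective, so the reading of these tables matters even though the tests are exploratory. For overall survival, SAP 8.2.4.4 warns that observation periods differ by HSCT status. The ADR comparisons carry no such warning.

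**Working it through.** **The plan's own figure.** The only design figure is the VOD/SOS power in Protocol 8.10.2. With 88 per group, 18.5% v 6.2% and two-sided alpha 0.1:

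z = (0.123 × √88 − 1.645 × √(2 × 0.1235 × 0.8765)) / √(0.185 × 0.815 + 0.062 × 0.938) = 0.85

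This gives 80.2% power; unrounded rates of 18.45% and 6.15% give the stated 80.4%. It reproduces, but says nothing about the three classes here.

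**Window by cycles.** From Protocol 8.2: doses on Days 1, 8 and 15, Cycle 1 of 21 to 28 days, later cycles of 28 days. For full cycles, window W = days before the last cycle starts + 14 + 28.

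| Full cycles | 1 | 2 | 3 | 4 | 5 | 6 |
|---|---|---|---|---|---|---|
| Cycle 1 = 21 d | 42 | 63 | 91 | 119 | 147 | 175 |
| Cycle 1 = 28 d | 42 | 70 | 98 | 126 | 154 | 182 |

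The range is about fourfold.

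**Equal hazard in both groups (assumed constant).** With 28-day risk r, P(c) = 1 − (1 − r)^(W/28), Cycle 1 = 21 days. The assumed overlapping mixes are:
- Group A: 35%, 35%, 20%, 10% with 1 to 4 cycles (mean 2.05).
- Group B: 20%, 30%, 25%, 15%, 5%, 5% with 1 to 6 cycles (mean 2.70).

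| r | B v A mixes | RR | 4 v 2 cycles | RR |
|---|---|---|---|---|
| 5% | 14.1% v 11.4% | 1.23 | 19.6% v 10.9% | 1.80 |
| 10% | 26.5% v 21.9% | 1.21 | 36.1% v 21.1% | 1.71 |
| 20% | 46.8% v 40.2% | 1.16 | 61.3% v 39.5% | 1.55 |
| 30% | 62.4% v 55.3% | 1.13 | 78.0% v 55.2% | 1.41 |

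The true hazard ratio is 1.00 in every row. With a 28-day Cycle 1 the mixes still give 1.13 to 1.23, and 4 v 2 gives 1.35 to 1.71.

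**Early events.** Let the hazard fall to a quarter after day 28, so that risk = 1 − exp{−h[28 + 0.25(W − 28)]} with h = −ln(1 − r)/28. Then 4 v 2 gives 1.35 (r = 10%) and 1.27 (r = 30%). If all first events fall within 28 days, the RR is 1.00. With a constant hazard and r = 80%, 4 v 2 gives 1.03.

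**Masking.** A two-cycle group with hazard 119/63 = 1.89 times that of a four-cycle group has the same proportion with an event, RR 1.00.

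**Against sampling error.** Take 88 per group and 30% v 35.1% (RR 1.17). SE(log RR) = √(0.649/(88 × 0.351) + 0.7/(88 × 0.3)) = 0.218, so the 95% CI is 1.17 × exp(±1.96 × 0.218) = 0.76 to 1.79. Such a contrast gives p < 0.1 in about 19% of studies, against a nominal 10%.

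**The 1.8 mg/m² factor.** SAP 5.4 counts it as present if any cycle qualifies. With an assumed chance of 10% per cycle, 1 − 0.9^c gives 10% at one cycle, 34.4% at four and 46.9% at six. More cycles raise both the factor and the window.

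**Why not events per patient-week.** Suppose two groups have windows of 10 and 18 weeks (two and four cycles, Cycle 1 = 28 days) and equal risk, with every first event in the first 4 weeks. The crude RR is correctly 1.00, but the rate ratio over the whole window is 10/18 = 0.56, a false protective effect.

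**The case against.** A reader might infer that groups with more cycles must show a higher risk by construction. The documents do not support that. It needs baseline groups that differ in cycles, and first events that continue past the shorter window; neither is documented. Protocol 8.2 ties cycle number to the HSCT schedule, not to age, ECOG PS or prior HSCT. Four against two cycles is not a planned contrast for these classes, so 1.4 to 1.8 is not an expected bias. Stopping because of an ADR works in the opposite direction, so even the net sign is uncertain.

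The proportion with an ADR over the whole treatment course is also a legitimate description of total risk. Cycle number arises after baseline and may lie on the path from a factor to an event. The risk ratio misleads only if it is read as a difference in on-treatment hazard, and no passage says which quantity is meant.

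There are safeguards. SAP 4.1 makes p-values descriptive, Protocol 8.14 admits that control of confounding may be inadequate, and SAP 8.2.3.5 allows additional analyses. A distortion of 1.1 to 1.2 lies well inside sampling error.

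All of this stands and limits the point. It does not remove it: exploratory status leaves the risk ratio and its interval affected, the limitations do not mention unequal windows, and no planned output lets the reader tell total risk from hazard.

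**Conclusion.** The point holds in a conditional form. The crude risk ratios for these three classes mix hazard with window length, and can show a difference where on-treatment hazards are equal or hide one where they differ.

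The size is modest on plausible assumptions: about 1.1 to 1.2 for overlapping cycle mixes, with 1.4 to 1.8 as the upper illustration. It is near 1.0 if first events are early, which may apply to myelosuppression. Infection and hemorrhage are more exposed if their risk persists through treatment. The factor for more than 1.8 mg/m² in a cycle is the most exposed of those listed. The hazards and cycle mixes are assumptions, because the documents give neither by subgroup. An addition to the SAP is worthwhile because a stated objective is affected and the cost is small.

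**What to change.** In SAP 8.2.3.4, for myelosuppression, infection and hemorrhage ADRs (any grade and Grade 3 or higher):

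- Add for each baseline factor a Kaplan-Meier comparison and Cox hazard ratio for time to first onset as in Section 8.1.4, censored at 28 days after the final dose as in Section 8.2.3.1.
- Report number of cycles and window length by subgroup.
- Keep the crude risk ratio as the description of total risk over the treatment course, and read it alongside the hazard ratio.
- Do not base the reading of a factor on events per patient-week, which assumes a constant hazard.
- State that the 1.8 mg/m² factor is not a baseline factor. A Cox model that treats it as known from the first dose would not repair it.

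Cost: SAP wording and more tables. Dosing dates (Protocol 8.8.3) and onset dates (8.8.14) are already collected, but events without an onset date cannot be used. Censoring at the end of treatment may be informative, since Protocol 8.8.4 lists AEs, progression and remission among the reasons for stopping. The result should therefore be labelled a sensitivity analysis within an exploratory plan.

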8.7. Observation Period

Observation period: The observation period will be 52 weeks for patients not undergoing HSCT within 52 weeks after the start of BESPONSA treatment or until 52 weeks following HSCT for patients undergoing it within 52 weeks after the start of BESPONSA treatment. For a patient starting BESPONSA treatment before 30 April 2020 who is transferred to another hospital during the observation period, the conclusion of the agreement on the implementation of this investigation should be requested to the hospital to which the patient has been transferred, and data from there should be collected to the extent possible.

(1) Treatment phase

From treatment initiation to Day 28 post-treatment: Safety (e.g., AEs) and efficacy (hematologic remission and survival)

(2) Follow-up phase

From Day 29 post-treatment to Week 52 (patients who did not undergo HSCT before Week 52) or 52 weeks after HSCT (patients who underwent HSCT before Week 52): Safety (VOD/SOS) and efficacy (survival)

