8.12.2. Analysis Methods

8.12.2.1. Analysis of Safety Endpoints

The occurrence of ADRs will be tabulated. In addition to an analysis using the entire safety set, analyses in subgroups stratified according to patient background characteristics will be carried out. The occurrence of liver disorder including VOD/SOS, myelosuppression, infections, hemorrhage, tumor lysis syndrome, infusion reaction, pancreatitis, interstitial lung disease, QTc interval prolonged, inflammatory gastrointestinal events and reproductive toxicity will be tabulated. For patients with special background characteristics such as children, elderly patients, pregnant women, patients with renal impairment and patients with hepatic dysfunction, the occurrence will be tabulated. Risk factors related to the development of VOD/SOS and risk factors related to early death of HSCT patients after BESPONSA treatment will be assessed.

The details of the analysis plan are specified in the SAP.

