### 5.4. Subgroups

Subgroup analyses of safety will be performed for the following patient characteristics. The subgroups defined for each background factor are shown in the squared brackets [] with the reference for the calculation of risk ratio/difference being underlined:

- Age [< 15 years, ≥ 15 to < 65 years, ≥ 65 years]
- Age [< 18 years, ≥ 18 to < 55 years, ≥ 55 years]
- Age [< 15 years, ≥ 15 to < 40 years, ≥ 40 years]
- Disease name [Relapsed CD22+ acute lymphocytic leukemia (ALL), refractory CD22+ ALL, other ALL, other]
- Chromosome karyotype [normal, t (4;11), unknown]
- Chromosome karyotype [Philadelphia chromosome positive, negative, unknown]\* Philadelphia chromosome is considered positive if the chromosome karyotype is t(9;22).
- Hepatic impairment [absent, present] {According to the Procedure of Extracting Patients with Hepatic Impairment/Renal Impairment in Post-Marketing Surveillance and its Attachment, the version of Medical Dictionary for Regulatory Activities Terminology (MedDRA) used for analysis should be followed.}
- Renal impairment [absent, present] (According to the Procedure of Extracting Patients with Hepatic Impairment/Renal Impairment in Post-Marketing Surveillance and its Attachment, the MedDRA version used for analysis should be followed.)
- Medical history (past) - VOD/SOS [absent, present]
- Medical history (past) - Graft versus host disease (GVHD) [absent, present]
- Medical history (past) - Hepatitis or hepatic disease [absent, present]

- Medical history (present) - VOD/SOS [absent, present]
- Medical history (present) - GVHD [absent, present]
- Medical history (present) - Hepatitis or hepatic disease [absent, present]
- Eastern Cooperative Oncology Group performance status (ECOG PS) before the start of this drug [0, 1,  $\geq 2$ , not performed]
- Aspartate aminotransferase (AST) and alanine aminotransferase (ALT) levels immediately before the start of this drug [ $\leq 1.5 \times$  the institutional upper limit of normal range (IULN), either  $> 1.5 \times$  IULN, not performed]
- $\gamma$ -glutamyl transpeptidase ( $\gamma$ -GTP) level immediately before the start of this drug [ $\leq 50$  IU/L,  $> 50$  IU/L, not performed]
- Total bilirubin level immediately before the start of this drug [ $\leq$  the institutional upper limit of normal range (IULN),  $>$  IULN, not performed]
- Hemoglobin level immediately before the start of this drug [ $< 10$  g/dL,  $\geq 10$  g/dL, not performed]

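### The GVHD-by-history analysis is not limited to patients at risk of GVHD in the event window, so its risk ratio mixes GVHD history with transplant status

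*SAP*

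**What the plan says.** SAP 8.2.3.4 ends its list of adverse drug reaction subgroup analyses with "Similarly, patients who experienced GVHD will be analyzed by each of the following factors". The two factors are past and present GVHD. The event is defined by coded term alone: "GVHD events included in the analysis will be events of which PT includes GVHD according to the version of MedDRA used for the analysis". The opening word carries over the preceding method, which is counts, proportions, risk ratios, a graph and a test. SAP 8.1.3 gives the effect measure: "For a comparison of proportion between subgroups, the risk ratio (RR) and its 95% CI will be determined".

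SAP 5.4 defines the past-history factor with two levels: "Medical history (past) - Graft versus host disease (GVHD) [absent, present". Present history has the same two. Neither factor has a level for patients without an earlier transplant.

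SAP 8.2.3.4 names no population for this analysis. The natural reading is the safety analysis set, in line with Protocol 8.12.2.1: "In addition to an analysis using the entire safety set, analyses in subgroups stratified according to patient background characteristics will be carried out".

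The window is set in SAP 8.2.3: "for ADRs and AEs other than VOD/SOS, those that occurred from the start of this drug to 28 days after the final dose". In Protocol 8.7 the later follow-up phase covers only "Safety (VOD/SOS) and efficacy (survival").

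**The concern.** GVHD presupposes a transplant. Everyone with a GVHD history has therefore had one, and can have GVHD again while on the drug. The absent group pools two kinds of patient: those with an earlier HSCT but no GVHD, and those with no earlier HSCT. The second kind can contribute an event only if transplanted between the first dose and Day 28 after the last.

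The comparison is therefore partly one of transplanted with untransplanted patients. A ratio well above 1 could be reported as evidence that earlier GVHD predicts GVHD on BESPONSA when history has no effect at all.

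The SAP limits comparable analyses to those at risk. VOD/SOS with HSCT after the start of the drug (8.2.3.1) and death after HSCT (8.2.3.3) use transplant recipients only. The GVHD analysis has no such limit.

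**Working it through.** The documents give no figure for the GVHD analysis. Their only computed design figure, 80.4% power with 176 patients, reproduces (80.2% from the rounded rates 18.5% and 6.2%, 80.4% from 18.45% and 6.15%). It concerns VOD/SOS and does not bear on this point.

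**Inputs**
- N = 176 in the safety analysis (Protocol 8.10.1).
- h = share with an allogeneic HSCT before the drug. Not in the documents; assumed.
- k = share of those with past GVHD. Not in the documents; assumed.
- Absent taken as the reference category. SAP 5.4 marks references by underlining, which the text as read does not show.

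**Expected ratio when history has no effect and there is no HSCT in the window**

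All Nhk patients with history are at risk. Of the N(1 − hk) without history, Nh(1 − k) are at risk. The at-risk share of the absent group is s = h(1 − k)/(1 − hk), and the expected ratio is 1/s. N cancels.

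| h | k | History present | Absent | Absent and at risk | s | Ratio 1/s |
|---|---|---|---|---|---|---|
| 40% | 50% | 35.2 | 140.8 | 35.2 | 0.25 | 4.0 |
| 60% | 30% | 31.7 | 144.3 | 73.9 | 0.51 | 1.95 |
| 25% | 70% | 30.8 | 145.2 | 13.2 | 0.09 | 11.0 |

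The last two rows are the extremes over h = 25–60% and k = 30–70%. The ratio should be 1.0 throughout. With the reference reversed, 4.0 becomes 0.25, which is the same distortion.

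**Effect on the test**

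Fisher's exact test was enumerated with history having no effect and no HSCT in the window. With 35 patients with history, 35 at risk without it, 106 not at risk, and a 10% GVHD risk in those at risk, p < 0.05 occurs in 40% of datasets. Restricted to the 70 at-risk patients, it occurs in 1.3%. Over h = 20–60%, k = 50% and GVHD risk 5–20%, the unrestricted figure runs from 13% to 74% and the restricted one from 0.3% to 3.2%.

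**Allowing HSCT in the window** (h = 40%, k = 50%, so one quarter of the absent group has an earlier HSCT)

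Let g be the GVHD risk from the earlier transplant, a the risk after a new one, and q1 and q0 the shares newly transplanted in the window with and without an earlier HSCT. The risk with history is q1·a + (1 − q1)·g. The risk in the absent group is 0.25 times that, plus 0.75·q0·a.
- g = a = 10%, q1 = q0 = 10%: 0.100 / (0.025 + 0.0075) = 3.1.
- g = 5%, a = 30%, q1 = 5%, q0 = 20%: 0.0625 / (0.0156 + 0.045) = 1.03.
- As the previous line, with q0 = 30%: 0.0625 / (0.0156 + 0.0675) = 0.75.

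**Present GVHD**

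If 10% of the 70 earlier recipients have present GVHD (assumed), the ratio is (176 − 7)/(70 − 7) = 169/63 = 2.7. A category of 7 falls under the 10-patient threshold in SAP 8.2.3.4, so that ratio may not be reported.

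**The case against.** A reader might infer that most of the absent group cannot have GVHD and that the ratio must be inflated. The documents do not support that.
- They give no share for earlier HSCT, GVHD history or HSCT in the window. At h = 60% and k = 30%, about 51% of the absent group is at risk. Fewer than half are at risk only if h is below 0.5/(1 − 0.5k), which is 59%, 67% or 77% for k = 30%, 50% or 70%.
- HSCT in the window is possible. SAP 5.4 plans a class of under 4 weeks from final dose to first HSCT. As shown above, such transplants can cancel or reverse the bias.

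A reader might also take the overall proportion as GVHD risk after BESPONSA and HSCT, or conclude that later GVHD is never captured. The SAP does not label the proportion that way and states the window openly. Protocol 10.2 keeps drug-related serious events reportable after the treatment phase, and SAP 8.2.3 puts all reported events in the listings. Later GVHD is outside the summarised window, which is not the same as uncollected.

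There are mitigating features. SAP 4.1 makes all tests exploratory. GVHD is neither a listed safety specification nor a named objective. Adverse drug reactions are also tabulated by earlier HSCT, and Protocol 8.14 concedes limited control of confounding.

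These points limit the consequence and stand. None corrects the estimate: the ratio is reported whatever the status of the p-value, and a separate table by earlier HSCT does not adjust it. The 10-patient rule gives no protection for past GVHD when both categories are large.

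**Conclusion.** The point holds in this form: the GVHD-by-history comparison has no at-risk restriction, so its risk ratio mixes history with transplant status. The size is about 1/s: 4.0 in the central example and about 2 to 11 over the range shown. This rests on assumed shares, no HSCT in the window, absent as the reference, and the safety analysis set as the population, which is inferred. The bias is usually upward, but it can vanish or reverse if in-window transplants are more common in patients without an earlier HSCT.

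Confidence is high that the restriction is missing, and moderate on direction and size. The impact is modest because the analysis is exploratory and concerns no listed safety specification. The change is still worth making, because it is cheap and removes the bias.

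**What to change.** In SAP 8.2.3.4:
1. Compute the history risk ratio and test among safety analysis set patients with an allogeneic HSCT before the drug, counting GVHD with onset before any later HSCT. State how unknown HSCT type is handled.
2. Tabulate GVHD after an in-window HSCT separately, so that these events are not lost. Alternatively, include those recipients and stratify by HSCT before the drug versus in the window.
3. State that the result does not estimate GVHD after post-drug HSCT in general.
4. State whether GVHD here means all adverse events or only adverse drug reactions; the text leaves this open.

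This needs a few sentences and a filter on HSCT type and dates, which are already collected. The cost is precision. In the central example the denominator falls from 176 to about 70, and at a 10% risk about 3.5 events are expected in each group of 35, so the interval will be wide. The patients left out carry no information on whether earlier GVHD predicts GVHD on the drug.
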